16.0 SAMPLE SIZE JUSTIFICATION AND INTERIM ANALYSIS FOR FUTILITY

In the ACOSOG Z1031 study, 16% of the patients in the letrozole alone arm had a PEPI score of 0. The sample size of this trial was determined with the assumption that 16% of the patients letrozole will have a PEPI 0 score. Assuming that addition of LEE011, either 600 mg for 21/7 scheme (Arm B) or 400mg for 28/28 scheme (Arm C), will increase the rate of PEPI 0 by 20%, and setting Type I error rate of 10% and Type II error rates at 20% (Rubinstein et al., 2005) in the final analysis with an interim analysis at 0.5 information time for futility, a sample size of 80 women in the treatment arms (40 in each arm) and 40 women in the control arm are needed to achieve 80% power in a 1-sided unpooled z-test with continuity correction for H_a : 36% vs. H_0 : 16%. This calculation was performed on nQuery + nTerim 3.0 using the O'Brian-Fleming spending function, and finds the drift parameter value of 2.224 and the futility lower bound of 0.0876.

Because the total sample size is estimated to be $80 + 40 = 120$ patients, the planned 0.5 information time for futility requires $120 \times 0.5 = 60$ patients. If the z-statistic is below the aforementioned lower bound 0.0876, the study will be stopped early for futility.

16.1 Accrual rate and study duration:

It is anticipated that 6 subjects per month will be enrolled. Accrual will be completed in 19 months. Pathology data will be available on the last subject 6 months after the accrual is complete. The trial should be completed for the primary endpoint analysis in 26 months after accrual is initiated.

16.2 Data Analysis Plans:

Although the trial is designed with 3 arms, the hypotheses concern about the comparisons of the two treatment arms combined vs. the control, hence 2-sample methods are planned.

The primary endpoint

The frequency and proportion of patients with PEPI score 0 at surgery will be reported for each arm. The 1-sided 90% confidence intervals (CI) will also be computed for the difference of proportions. The proportions will be compared between treatment (Letrozole with 2 ribociclib arms combined) and control by 1-sided unpooled z-test with continuity correction for both the interim futility and the final analyses at 0.02 and 0.094 significance level, respectively, to retain a cumulative 0.10 significance level. The trial will be stopped early if the z-value in the futility analysis is below the boundary of 0.0876.

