The secondary endpoints

The secondary objectives concern about four endpoints. Among them, the three binary endpoints (Complete cell cycle arrest, pCR, cCR) will be analyzed in the same way as the primary endpoint described above but they will not be analyzed for futility.

The Ki-67 level is often skewed in its distribution and will be summarized by median and corresponding 95% CI (use e.g. the CIPCTLDF option in PROC UNIVARIATE, SAS) for each arm. The Ki-67 may take zero values and will be square-root transformed, and compared between arms by 1-sided 2-sample t-test, or by Wilcoxon rank-sum test if transformations fail to make distributions approximately normal.

The 5-year relapse-free survival and corresponding confidence interval will be estimated by Kaplan-Mayer estimator for each arm, and compared between treatment arms combined vs. control by 1-sided log-rank test.

Significance for the secondary endpoints will be assessed at 0.05 significance level.

In addition, we will explore differences between the two treatment doses by 2-sided Fisher's exact test, 2-sided t- or Wilcoxon test, and 2-sided log-rank test at 0.05 significance level.

Interim analysis

Since the patient accrual was almost complete by the time first 60 patients had complete information regarding PEPI scores, interim analysis will not be performed.

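### The final primary test is still set at one-sided 0.094 for an interim look that will not take place, so it matches neither the stated 10% Type I error nor the 90% confidence interval; the effect is small and conservative.

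*Combined protocol and SAP*

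**What the plan says.** Section 16.0 sets a one-sided Type I error of 10% and a Type II error of 20%, with one futility look at half information and an O'Brien-Fleming spending function. Assuming 16% versus 36%, it concludes that 40 controls and 80 ribociclib patients (both arms combined) "are needed to achieve 80% power in a 1-sided unpooled z-test with continuity correction".

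Section 16.2, under the primary endpoint, gives three further rules:

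- The test is applied "for both the interim futility and the final analyses at 0.02 and 0.094 significance level, respectively, to retain a cumulative 0.10 significance level".
- "The 1-sided 90% confidence intervals (CI) will also be computed for the difference of proportions". No method is named for this interval.
- "The trial will be stopped early if the z-value in the futility analysis is below the boundary of 0.0876". Section 16.0 carries the same rule.

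The last paragraph of Section 16.2 reports that accrual was nearly finished when the first 60 patients had PEPI data, and that the "interim analysis will not be performed". Neither section says which level then governs the one remaining test.

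**The concern.** The stated reason for 0.094 is that 0.02 and 0.094 together accumulate to 0.10. Once the first look is dropped, nothing accumulates and the reason is gone. It was weak even before that: the look is described only as a futility look, with a lower stopping bound and no rule for stopping on efficacy. A look that cannot reject the null hypothesis uses no Type I error.

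What is at stake is the success threshold for the only primary hypothesis. If the p-value falls between 0.094 and 0.10, one reader can cite the 10% error rate and the 90% interval for success, and another can cite 0.094 for failure. Settling that after the data are seen would be a post hoc decision on the primary result.

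The mismatch between interval and test does not depend on the cancellation. A one-sided 90% interval never corresponded to a 0.094 test.

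**Working it through.** **Inputs.** From Section 16.0: one-sided alpha 0.10, beta 0.20, information time 0.5, O'Brien-Fleming spending, rates 16% and 36%, 40 control and 80 treated, unpooled z with continuity correction. From Section 16.2: levels 0.02 and 0.094, bound 0.0876, one-sided 90% interval.

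**1. Reproducing the plan's levels.**

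- Interim spend: 2[1 − Φ(z(0.95)/√0.5)] = 2[1 − Φ(1.6449/0.7071)] = 0.0200, so the interim bound is z = 2.054.
- The final bound u solves P(Z1 < 2.054, Z2 ≥ u) = 0.10 − 0.0200 under the null, with correlation √0.5. This gives u = 1.3165, nominal level 0.0940.
- Futility: the same function with beta 0.20 spends 0.0699 at the look. With non-binding futility and the efficacy bounds above, the required drift is 2.212 and the lower bound is Φ⁻¹(0.0699) + 2.212 × 0.7071 = 0.0876.

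The 0.02, the 0.094 and the 0.0876 all reproduce, so 0.094 is the residue of an efficacy spend. The plan states a drift of 2.224 against my 2.212. I cannot explain the difference, but it does not affect this point.

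**2. Critical value without the look.** A single one-sided test at 0.10 needs z = 1.2816. At 0.094 it needs z = 1.3165. The unused nominal error is 0.10 − 0.094 = 0.006.

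**3. Power at 40 versus 80, normal approximation.**

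- SE = √(0.16 × 0.84/40 + 0.36 × 0.64/80) = 0.0790
- Continuity correction = 0.5(1/40 + 1/80) = 0.01875
- Corrected drift = (0.20 − 0.01875)/0.0790 = 2.294
- Power at 0.10 = Φ(2.294 − 1.2816) = 84.4%
- Power at 0.094 = Φ(2.294 − 1.3165) = 83.6%

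**4. Exact enumeration of the 40 versus 80 table, corrected test.**

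| | 0.094 | 0.10 |
|---|---|---|
| Power, 16% vs 36% | 82.5% | 83.5% |
| Size, common rate 16% | 0.0766 | 0.0766 |
| Size, common rate 20% | 0.0759 | 0.0764 |

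The probability under the design alternative of falling between the two critical values is 0.99%.

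**5. Interval against test.** Take 8/40 versus 26/80, that is 20.0% versus 32.5%.

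- SE = √(0.20 × 0.80/40 + 0.325 × 0.675/80) = 0.0821
- z = (0.125 − 0.01875)/0.0821 = 1.294, p = 0.098
- Lower 90% limit with the same SE and correction: 0.10625 − 1.2816 × 0.0821 = +0.001, which excludes zero
- The 0.094 test fails, because 1.294 < 1.3165

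A 0.094 test corresponds to a 90.6% interval.

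**6. If the interval were an uncorrected Wald interval (an assumption, as no method is given).** Under the alternative it would exclude zero while the 0.094 test fails in 5.62% of trials. With the test at 0.10 the conflict remains in 5.62% − 0.99% = 4.63%. Only the 0.99% comes from the level. The rest comes from pairing an uncorrected interval with a corrected test.

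**The case against.** The best defence is that 0.094 is a pre-specified level below the overall alpha, and therefore valid. It costs about one point of power and leaves power above the planned 80%. Relaxing it when accrual is nearly complete makes success slightly easier, so leaving it alone is the cautious course. The leftover 0.0876 rule cannot be triggered, because the plan says that the look will not happen. Few tables are affected: with 2 to 13 control responders, only 8/40 versus 26/80 and 12/40 versus 35/80 lie between the two thresholds, so the example is not typical.

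Most of this stands. It limits the severity, and it makes a deliberate 0.094 a coherent alternative. It does not remove the contradiction, because the plan nowhere says that 0.094 is being kept on purpose. It still ties that level to a cumulative 0.10 and still pairs it with a 90% interval.

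A reader might also infer that the interval and the test would disagree in about 5.6% of trials because of the 0.094 level. The documents do not support that. The figure needs an assumed uncorrected interval, and 4.6 points of it would persist at 0.10.

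**Conclusion.** The point holds, at minor to moderate severity. The single remaining primary test is tied to a level whose stated justification no longer applies, and that level conflicts with the 10% Type I error and with the 90% interval. The numerical effect is small and conservative: 0.006 of nominal error, 0.8 points of asymptotic or 1.0 point of exact power, and about 1% of trials under the alternative between the thresholds.

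Three stronger readings are not supported:

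- **Inflated error or an invalid test.** A test at 0.094 stays below 0.10. At a common 16% rate the continuity correction holds actual size at about 0.077 under either level.
- **Loss of the planned power.** The stated 80% was derived for a two-look design, but the fixed 40 versus 80 design exceeds it at both levels.
- **Interim alpha already used.** The plan says that the look will not be done, and Section 13.3 keeps the blind until database lock. That no comparative interim data were seen is an inference from these two statements; neither says so directly.

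The figures assume the design rates, exactly 40 and 80 evaluable patients, and the unpooled corrected test as specified.

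**What to change.** Before unblinding, amend Sections 16.0 and 16.2 as follows:

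1. State that there is one final analysis of the primary endpoint at one-sided 0.10 (critical z 1.2816), in line with Section 16.0 and the 90% interval. If the sponsor prefers to keep 0.094, say that this is deliberate and report a one-sided 90.6% interval.
2. Specify that the interval uses the same unpooled standard error and continuity correction as the test. Matching the level alone would not make an uncorrected Wald interval agree with the test.
3. Delete the 0.02 level and the 0.0876 stopping rule from the operative text, and keep the sentence that explains why the interim was dropped.
4. Restate power at 0.10 for the fixed 40 versus 80 design as about 84% (83% by exact enumeration).

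The cost is wording only. Sample size, patient procedures and data collection do not change. Recording the choice before database lock keeps it from being made with the result in view.

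### For the three binary secondary endpoints, the inherited one-sided 90% interval does not match the 0.05 level at which significance is judged, and that level's sidedness is left to inference

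*Combined protocol and SAP*

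**What the plan says.** All the relevant text is in the combined protocol and SAP, section 16.2 (Data Analysis Plans).

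- **Primary endpoint, interval:** "The 1-sided 90% confidence intervals (CI) will also be computed for the difference of proportions".
- **Primary endpoint, test:** arms B and C combined are compared with arm A "by 1-sided unpooled z-test with continuity correction for both the interim futility and the final analyses".
- **Primary endpoint, levels:** the interim look is allotted 0.02 and the final look 0.094, so that the total over both is 0.10.
- **Secondary endpoints, method:** complete cell cycle arrest, pCR and cCR "will be analyzed in the same way as the primary endpoint described above but they will not be analyzed for futility". Futility is the only exception.
- **Secondary endpoints, level:** "Significance for the secondary endpoints will be assessed at 0.05 significance level". Sidedness is not given in that sentence. The Ki-67 and log-rank comparisons above it are called one-sided; the dose comparisons that follow it are called two-sided.
- **Interim analysis:** the closing paragraph of 16.2 says that the interim look will not take place.

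The only 95% interval in the secondary-endpoint text is for the median Ki-67 in each arm. None is given for a difference of proportions.

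**The concern.** The primary analysis consists of per-arm proportions, a one-sided 90% interval for the difference, and a one-sided corrected z-test. Carrying it over with futility as the only exception carries the interval over too. The later 0.05 sentence speaks of significance only and does not replace the interval. The plan therefore pairs an interval at alpha 0.10 with a decision at 0.05.

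Complete cell cycle arrest at day 14 is listed first among the secondary endpoints in section 2.5. If its result is borderline, the report would show an interval wholly above zero beside a test that does not reject. Readers tend to take an interval that excludes zero as evidence of effect at the trial's stated level. Here it would be evidence only at twice that level. Settling the pairing before the data are seen removes a choice of presentation afterwards.

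**Working it through.** **Inputs from the plan.** 80 patients on ribociclib and 40 on control (section 16.0); one-sided unpooled z-test with continuity correction, one-sided 90% interval, levels 0.02 and 0.094 (16.2, primary endpoint); 0.05 for secondary endpoints (16.2). The documents give no expected rates for the three binary secondary endpoints, so every rate used for them below is an assumption.

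**1. The plan's own primary figures.**
- Sample size for 16% v 36%, 2:1, one-sided 0.10, 80% power. The weighted mean rate is (0.16 + 2 × 0.36)/3 = 0.2933. Without correction, control n = [1.2816 × √(1.5 × 0.2933 × 0.7067) + 0.8416 × √(0.1344 + 0.2304/2)]² / 0.20² = 32.2. With correction, n′ = (32.2/4) × [1 + √(1 + 3/(32.2 × 0.20))]² = 39.4, rounded up to 40. This gives 40 + 80 = 120, as stated. (This is the pooled-null formula; the fully unpooled version with correction gives 36 controls, so 40 is adequate.)
- Levels. O'Brien-Fleming-type spending of 0.10 at half the information gives 0.0200. Two looks with correlation √0.5, tested at 0.02 and 0.094, give a cumulative 0.09999. So 0.094 is what remains for a final look after 0.02 has been allotted to an interim look.

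**2. What each level implies.** Let d be the observed difference, c = 0.5 × (1/80 + 1/40) = 0.01875 the correction, and SE the unpooled standard error. The test statistic is z = (d − c)/SE, and the lower limit with the same correction is d − c − z(1−α) × SE. That limit is above zero exactly when one-sided p is below α. A one-sided 90% limit therefore answers a 0.10 test (1.2816), and a one-sided 0.05 test needs a 95% limit (1.6449). The two disagree whenever 0.05 < p < 0.10.

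**3. Worked example, assuming 20/40 control responders.** For 52/80: d = 0.650 − 0.500 = 0.150; SE = √(0.25/40 + 0.65 × 0.35/80) = 0.0954; z = (0.150 − 0.01875)/0.0954 = 1.376.

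| Ribociclib | One-sided p | 90% lower limit | 95% lower limit |
|---|---|---|---|
| 51/80 | 0.107 | −0.4 points | −3.8 points |
| 52/80 | 0.084 | +0.9 points | −2.6 points |
| 53/80 | 0.065 | +2.2 points | −1.3 points |
| 54/80 | 0.0497 | +3.5 points | +0.03 points |

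At 52/80 and 53/80 the carried-over interval excludes zero while the 0.05 test does not reject. At 54/80 the sidedness matters: the result is significant at one-sided 0.05 but not at two-sided 0.05 (2 × 0.0497 = 0.099).

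**4. How often this happens.** Exact enumeration over Binomial(80) × Binomial(40) gives the probability of 0.05 < p < 0.10:

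| Assumed truth (control v ribociclib) | Probability |
|---|---|
| No difference, common rate 10%, 16%, 30%, 50% | 4.2%, 3.6%, 3.7%, 3.3% |
| 16% v 36% (the primary endpoint's design rates) | 9.4% |
| 50% v 70% | 11.3% |
| 10% v 20% | 12.6% |
| 50% v 65% | 13.2% |
| 30% v 45% | 13.3% |
| 60% v 75% | 14.1% |
| 50% v 80% | 3.7% |
| 50% v 90% | 0.1% |

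**The case against.** A reader might infer that the plan leaves two live test levels, 0.094 and 0.05, so that a result with p = 0.08 is both significant and non-significant and the analyst may choose. The documents do not support this. The 0.05 sentence comes later, is specific to secondary endpoints and has no exceptions, so it governs the general cross-reference. The 0.094 exists only to offset an interim look from which these endpoints were excluded and which 16.2 cancels. For the same reason, the roughly doubled null exclusion rate (0.069-0.081 at the 0.10 cut, against 0.036-0.041 at 0.05, for common rates of 10%, 30% and 50%) is not an error rate of this plan: no sentence tests these endpoints at 0.10.

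It can also be said that the interval has no decision role, and that a limit labelled 90% is an honest description. That is true, and it keeps the point minor. It does not make the pairing sensible, because nothing in the plan explains why the interval should use twice the alpha of the decision.

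Two cautions on size also stand:

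- The 13-14% figures sit near the maximum. The band narrows to 9.4% at 36% v 16% and almost vanishes for large effects. Section 1.7 describes pCR after endocrine therapy as very rare, so the 20/40 example cannot represent that endpoint.
- The plan specifies the correction for the test, not for the interval. Without it, the 95% lower limit at 53/80 is 0.1625 − 1.6449 × 0.0951 = +0.6 points, so that row depends on the choice. The 52/80 row does not: uncorrected, its limits are 0.150 − 1.2816 × 0.0954 = +2.8 points and 0.150 − 1.6449 × 0.0954 = −0.7 points.

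**Conclusion.** The concern holds as an interval-and-test mismatch. Significance for the three binary secondary endpoints is set at 0.05; one-sided is the natural reading, but it rests on the cross-reference to the primary method and on the neighbouring one-sided tests. The only interval specified for the difference corresponds to 0.10. A result with one-sided p between 0.05 and 0.10 is non-significant under the plan, yet its reported interval would exclude zero. With 80 v 40 patients the chance of this is about 3-4% per endpoint under no difference and about 9-14% for the assumed moderate effects. These figures assume full enrolment with complete data, the corrected unpooled z-test, the same correction in the interval, and rates that the documents do not supply. Severity is minor: the primary analysis, the sample size and the secondary decision level are unaffected.

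**What to change.** In the secondary-endpoint paragraph of 16.2, replace the general cross-reference with wording such as: *Complete cell cycle arrest, pCR and cCR will be compared between the combined ribociclib arms and control by the unpooled z-test with continuity correction at one-sided 0.05, with a one-sided 95% (equivalently two-sided 90%) confidence interval for the difference of proportions computed with the same correction. The 0.02 and 0.094 levels and the one-sided 90% interval apply to the primary endpoint only.*

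The cost is a short wording change and a slightly lower confidence limit. In the 52/80 example the limit moves from +0.9 to −2.6 points, a drop of (1.6449 − 1.2816) × 0.0954 = 3.5 points. No patients, data or new methods are needed.

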2.0 STUDY OBJECTIVES AND ENDPOINTS

2.1 Primary Objective:

- To determine if ribociclib in combination with letrozole as a 24 week neoadjuvant endocrine therapy increases the proportion of women with PEPI score of 0 at surgery compared to patients treated with placebo and letrozole therefore allowing more patients to have excellent outcomes without chemotherapy.

2.2 Secondary Objectives:

- To determine if ribociclib in combination with letrozole as a 24 week neoadjuvant endocrine therapy increases the proportion of tumors with complete cell cycle arrest (defined below) compared to placebo and letrozole therefore increasing the number of women who would have excellent outcomes with endocrine therapy alone.
- To determine if ribociclib in combination with letrozole for 24 weeks results in improved 5 year RFS compared to letrozole alone.
- To examine the differences in clinical, pathologic and radiologic response rates between the two ribociclib containing arms (combined) vs letrozole. An increase in response rate

with the addition of ribociclib will be an indication of synergistic activity of ribociclib when combined with letrozole and will help design future adjuvant trials.

- To examine the difference in clinical, pathologic and radiologic response as well as PEPI scores between the three treatment arms.
- To examine if short term Ki67 expression at 2 weeks and degree of Ki67 suppression compared to baseline differs between the two ribociclib containing arms (combined) vs letrozole.

2.3 Exploratory Objectives:

- To evaluate tumor tissue, serum, and plasma specimens collected at baseline, on-therapy, and at surgery for biomarker discovery (through methods such as gene expression profiling, DNA and RNA sequencing and proteomics) in studies that aim to understand signaling pathways associated with endocrine therapy sensitivity and pathways of resistance.

2.4 Primary Endpoint:

- Rate of PEPI score 0 at surgery between ribociclib containing arms (combined) vs letrozole alone arm. PEPI score 0 is defined as:
 - pT stage 0, 1 or 2 at surgery, after 24 weeks of neoadjuvant therapy
 - Negative axillary lymph nodes present at surgery
 - Ki67 of $\leq 2.7\%$ at surgery
 - Tumor is ER+ at surgery.

2.5 Secondary Endpoints:

- Rate of complete cell cycle arrest at 2 weeks between ribociclib containing arms (combined) vs letrozole alone arm: Complete cell cycle arrest is defined as Ki67 at day 14 of $\leq 2.7\%$.

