9.0 Sample collection and storage for future correlative studies

Tissue samples will be collected and stored as below, at baseline, Day 14 (+7) of Cycle 1, and at the time of surgery for biomarker analysis including ER and Ki67 and for future correlative studies. In addition, blood will be collected for serum, plasma, and germ-line and cell free DNA and stored at baseline for future correlative studies. The correlative studies will be performed in collaboration with [name] at the Siteman Cancer Center and [name] and [name] at the City of Hope Comprehensive Cancer Center.

Sample Collection/Shipment Kit

The kit is a two-chamber kit in which it is possible to ship both frozen and ambient specimens. The kit is stocked with necessary items needed for blood and tumor sample collection. It also contains the necessary materials used to process and prepare specimens for shipment in accordance to IATA regulations.

Washington University Tissue Procurement Core Facility (WUTPC)
[name]
[name]
[contact]
Email: [contact]

Sample collection/shipment kits are available for institutions by sending the request to Email: [contact] with the subject "FELINE Trial Biopsy Kit Request".

9.1 Required pre-treatment core biopsy for biomarker and correlative studies:

Samples collection is mandatory for all patients prior to initiating study therapy.

Core biopsy should be performed with image guidance using a 14 gauge needle. The required biopsies include two core biopsies placed in 10% buffered formalin (a single pre-filled formalin container to hold both cores) and two core biopsies frozen **immediately at bedside** in separate OCT blocks. The cryo kits, formalin containing cup and blood collection tubes will be provided in the sample collection/shipment kits to the sites and are funded by this study.

Tissue may be obtained concurrent with another procedure (clip placement, axillary node biopsy, port placement) or as a separate procedure.

9.2 Required Day 14 (+7) core biopsy for biomarker and correlative studies:

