9.6.1 Baseline and Day 14 (+7d)

Upon receipt of the specimen, the 2 fixed biopsy specimens at baseline and 2-week will be further processed for tumor Ki67 analysis at the CLIA certified Anatomic and Molecular Pathology Core Labs at Barnes Jewish Hospital at St. Louis (CLIA number 26D2013203). After embedding in paraffin, one section from the tumor block will be stained with H&E to assess biopsy adequacy. Another section from the block will be incubated with antibody against Ki67 (clone 30-9) and then assayed using the Ventana Benchmark platform. The block and any remaining sections will be returned to the Tissue Procurement Core Facility at the completion of testing. Both cores will be reviewed and will be taken into account for the scoring.

Ki67 scoring is reported as a quantitative/continuously distributed value. The Ki67 data for Day 14 biopsy is available real time to the treating physician and the patients. Patients will be continued on protocol therapy while awaiting analysis results. Results of tumor Ki67 will be reported within 10 working days upon receipt of the samples. Wash U Coordinator will email and fax the results to both the CRA listed on Specimen Submission CRF that is sent with the tissue samples and Wash U CRA. Contact Wash U coordinator for questions related to the Ki67 result.

Note: If the biopsy yielded no tumor cells, the patient may continue on study drug therapy or proceed with a second biopsy for Ki67 determination.

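### The continuous Ki67 comparison leaves out baseline Ki67, names no time point, and gives the suppression-from-baseline part of the objective no defined measure

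*Combined protocol and SAP*

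**What the plan says.** The last secondary objective in section 2.2 has two parts: Ki67 expression at 2 weeks, and whether the "degree of Ki67 suppression compared to baseline differs between the two ribociclib containing arms (combined) vs letrozole".

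The data for both parts are planned. Section 9.1 states of the pre-treatment cores: "Samples collection is mandatory for all patients prior to initiating study therapy". Section 9.6.1 states that "the 2 fixed biopsy specimens at baseline and 2-week will be further processed for tumor Ki67 analysis", in one certified laboratory with one antibody and platform, and that "Ki67 scoring is reported as a quantitative/continuously distributed value".

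Section 16.2, under the secondary endpoints, gives the only analysis of continuous Ki67. The level "will be summarized by median and corresponding 95% CI" for each arm. Then: "The Ki-67 may take zero values and will be square-root transformed, and compared between arms by 1-sided 2-sample t-test". A Wilcoxon test takes the place of the t-test when no transformation brings the data close to normality. Secondary tests use the 0.05 level.

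No baseline covariate, change score, percent reduction or ratio is defined anywhere. Section 16.2 does not say which Ki67 measurement is compared, although Ki67 is measured at baseline, day 14 and surgery.

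**The concern.** Two things are missing.

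First, if a patient's starting Ki67 predicts her day-14 value, an unadjusted test leaves that between-patient spread in its error term. Using baseline would remove part of it at no cost in tissue, visits or patients.

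Second, half of a stated objective has no measure. A later analyst would have to choose between absolute change, percent change and a ratio, and decide what to do with zeros, possibly after seeing the data. The unnamed time point adds another choice, and it matters: under section 4.3.3 patients with day-14 Ki67 above 10% leave study treatment, so day-14 and surgical Ki67 do not give the same comparison.

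At stake are the precision and interpretability of one secondary comparison.

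**Working it through.** **The plan's own figures.** The documents give no SD, effect size, correlation or power for Ki67, so there is no Ki67 figure to reproduce. The only design calculation is for PEPI 0 (section 16.0). The continuity-corrected two-proportion formula, with 16% vs 36%, one-sided 0.10, 80% power and 2:1 allocation, gives 40 + 80 = 120, as stated. Only the group sizes carry over to Ki67.

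**Inputs.** 80 patients (B+C) vs 40 (A), from section 16.0; one-sided 0.05, from section 16.2. Assumed: the correlation r between square-root baseline and square-root day-14 Ki67, shown over a range. Effects are in units of the SD σ of square-root day-14 Ki67.

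**Planned t-test.** SE = σ√(1/80 + 1/40) = σ√0.0375 = 0.194σ. Power of 80% needs a difference of (1.645 + 0.842) × 0.194σ ≈ 0.48σ.

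**ANCOVA with baseline as covariate.** Under a linear model with a common slope and complete pairs, variance is multiplied by 1 − r². The equivalent size of the planned test is 120/(1 − r²).

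**t-test on raw change.** If baseline and day-14 SDs are equal, variance is multiplied by 2(1 − r).

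| r | ANCOVA variance factor | Equivalent N | ANCOVA power at 0.48σ | Change-score factor | Change-score power at 0.48σ |
|---|---|---|---|---|---|
| 0 | 1.00 | 120 | 80.0% | 2.0 | 54.5% |
| 0.3 | 0.91 | 120/0.91 = 132 | 83.2% | 1.4 | 67.6% |
| 0.5 | 0.75 | 120/0.75 = 160 | 89.0% | 1.0 | 80.0% |
| 0.6 | 0.64 | 120/0.64 = 188 | 92.8% | 0.8 | 87.2% |

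The planned t-test has 80% power in every row. With equal SDs a raw change score is therefore worse than the current plan when r < 0.5. If the baseline SD is k times the day-14 SD, the change-score factor is 1 + k² − 2rk, which exceeds 1 when r < k/2. At k = 1.5 that is r < 0.75.

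**What the planned test targets.** Randomization gives the arms the same expected square-root baseline Ki67. The expected arm difference in square-root day-14 Ki67 therefore equals the expected arm difference in square-root change. In the same way, ANCOVA has the same treatment coefficient whether the outcome is the day-14 value or the change. Adjustment alters the precision of that quantity, not its expected value under a common slope.

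**The case against.** The strongest reply concerns weight. Section 2.5 lists four secondary endpoints (cell cycle arrest, pCR, cCR and 5-year RFS), and continuous Ki67 is not among them. No sample size or decision rule rests on it. This stands and limits the point to a modest improvement.

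The gain is also uncertain. Section 16.2 itself expects skewed values and possible zeros. If day-14 values cluster near zero, r may be small, and at r = 0 nothing is gained. If ribociclib pushes values to the floor, the baseline slope may differ by arm, and with 2:1 allocation a main-effects ANCOVA is not guaranteed the tabulated gain. Nor will every patient necessarily have a pair: "If the biopsy yielded no tumor cells, the patient may continue on study drug therapy or proceed with a second biopsy for Ki67 determination". All of this stands.

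A reader might infer three stronger claims that the documents do not support:

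- **That the planned comparison is biased by chance baseline imbalance.** Randomization keeps it unbiased, and its standard error already allows for such imbalance.
- **That the test says nothing about suppression.** It already targets the mean difference in square-root change. What is missing is a defined measure, particularly on the percentage scale that section 1.4 uses for letrozole's earlier results (87% vs 75%).
- **That the t-test/Wilcoxon rule inflates type I error.** The criterion is vague, but the order is fixed and one test is designated. No inflation has been shown.

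The objection does not close the gap between sections 2.2 and 16.2, and it does not give a reason to leave an already planned baseline measurement unused.

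**Conclusion.** The point holds for a secondary objective. The planned Ki67 test is valid but leaves out a baseline value that the trial intends to collect and score centrally. The time point is unnamed, and the degree of suppression has no defined measure.

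The missing covariate and missing definition can be read directly from the documents. The size of the precision loss cannot: it runs from nothing at r = 0 to a 36% variance reduction at r = 0.6, given a common slope and complete pairs. The equivalent sample sizes illustrate what r would imply and should not be read as an established loss. The primary PEPI comparison and N = 120 are untouched.

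**What to change.** Revise the Ki67 paragraph in section 16.2 before unblinding:

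1. Name day 14 as the time point.
2. Make the main analysis an ANCOVA of square-root day-14 Ki67 on treatment (B+C vs A) with square-root baseline Ki67 as covariate. Because allocation is 2:1 and slopes may differ, use robust standard errors, or include a treatment-by-baseline interaction with baseline centred at its overall mean.
3. Define one descriptive suppression summary per arm, such as median percent change from baseline, with a stated rule for zeros.
4. Name one rank-based analysis as the sensitivity analysis, in place of the conditional switch.
5. State how patients without a scorable baseline or day-14 biopsy are handled.

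Do not substitute a t-test on raw change, which may be less precise than the present plan.

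The cost is one paragraph of the analysis plan and a few lines of code. No new sample, visit or patient is needed.
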